3. LIST OF ABBREVIATIONS AND DEFINITIONS OF TERMS

The following abbreviations and specialist terms are used in this study protocol.

Table 1: Abbreviations and Specialist Terms

Abbreviation or Specialist Term	Explanation
ACL	adenosine triphosphate-citrate lyase
ACS	acyl-CoA synthetase
ADR	adverse drug reaction
AE	adverse event
AESI	adverse events of special interest
ALB	albumin
ALK-P	alkaline phosphatase
ALT	alanine aminotransferase
ANCOVA	analysis of covariance
apoB	apolipoprotein B
ASCVD	atherosclerotic cardiovascular diseases
AST	aspartate aminotransferase
ATP	adenosine triphosphate
AUC ₀₋₂₄	area under the curve during 24 hours
BMI	body mass index
BP	blood pressure
BUN	blood urea nitrogen
Ca	calcium
CEC	Clinical Event Committee
CETP-I	Cholesteryl ester transfer protein inhibitor
CFR	Code of Federal Regulations
CHD	coronary heart disease
CI	confidence interval
CK	creatine kinase
Cl	chloride
C _{max}	time to peak maximum concentrations
CMV	cytomegalovirus
CNS	central nervous system
CoA	acetyl-coenzyme A
CO ₂	carbon dioxide
CRO	contract research organization

Table 1: Abbreviations and Specialist Terms

Abbreviation or Specialist Term	Explanation
CV	cardiovascular
CYP	cytochrome P450
DBP	diastolic blood pressure
DMC	Data Monitoring Committee
ECG	electrocardiogram
eCRF	electronic case report form
EMA	European Medicines Agency
eGFR	estimated glomerular filtration rate
EOS	end of study
ETC-1002-CoA	ETC-1002-coenzyme A
EU	European Union
FAS	full analysis set
FDA	U.S. Food and Drug Administration
FPFV	first patient first visit
FSH	follicle-stimulating hormone
GCP	good clinical practice
GI	gastrointestinal
HbA _{1C}	glycosylated hemoglobin, Type A _{1C}
HBsAg	hepatitis B surface antigen
Hct	hematocrit
HCV	hepatitis C virus
HCV-AB	hepatitis C antibodies
HDL-C	high-density lipoprotein cholesterol
Hgb	hemoglobin
HMG-CoA	3-hydroxy-3-methylglutaryl-coenzyme A
hs-CRP	high-sensitivity C-reactive protein
IB	investigator's brochure
ICD	informed consent document
ICH	International Conference on Harmonisation
IEC	independent ethics committee
IMP	investigational medicinal product
IND	Investigational New Drug Application
INR	international normalized ratio
IRB	institutional review board
ITT	intention-to-treat

Table 1: Abbreviations and Specialist Terms

Abbreviation or Specialist Term	Explanation
IWRS	interactive web response system
K	potassium
LDH	lactate dehydrogenase
LDL-C	low-density lipoprotein cholesterol
LDLR	low-density lipoprotein receptor
LFT	liver function test
LPLV	last patient last visit
LMT	lipid-modifying therapy
LS	least square
LSM	least square mean
MACE	major adverse cardiac event
MCH	mean corpuscular hemoglobin
MCHC	mean corpuscular hemoglobin concentration
MCV	mean corpuscular volume
MDRD	modification of diet in renal disease
MED ID	medication identification
MedDRA	Medical Dictionary for Regulatory Activities
MI	myocardial infarction
MRI	magnetic resonance imaging
Na	sodium
NIMP	non-investigational medicinal product(s)
NLA	National Lipid Association
NOAEL	No-observed-adverse-effect level
non-HDL-C	non-high-density lipoprotein cholesterol
NYHA	New York Heart Association
PCSK9	proprotein convertase subtilisin/kexin type 9
PE	physical exam
PK	pharmacokinetic(s)
PG	pharmacogenomic
PMM	pattern mixed model
PT	prothrombin time
RBC	red blood cell
RNA	ribonucleic acid
SAE	serious adverse event
SAP	statistical analysis plan

Table 1: Abbreviations and Specialist Terms

Abbreviation or Specialist Term	Explanation
SBP	systolic blood pressure
SE	standard error
SGOT	serum glutamic oxaloacetic transaminase
SGPT	serum glutamic pyruvic transaminase
siRNA	small interfering ribonucleic acid
SOC	system organ class
SOP	standard operating procedures
SP	safety population
SUSARS	suspected and unexpected serious adverse reactions
$t_{1/2}$	terminal elimination half-life
T2DM	type 2 diabetes mellitus
TB	total bilirubin
TC	total cholesterol
TEAE	treatment-emergent adverse event
TG	triglycerides
TSH	thyroid-stimulating hormone
TQT	thorough QT/QTc
ULN	upper limit of normal
US	United States
WBC	white blood cell
WHO	World Health Organization

4. INTRODUCTION

4.1. Lipid-Regulating Drugs and Cardiovascular Disease

Bempedoic acid (ETC-1002) is an inhibitor of adenosine triphosphate-citrate lyase (ACL) (adenosine triphosphate [ATP] citrate lyase), an enzyme upstream of 3-hydroxy-3-methylglutaryl coenzyme A (HMG-CoA) reductase in the cholesterol biosynthesis pathway. It is an oral, first-in-class small molecule designed to lower low-density lipoprotein cholesterol (LDL-C) levels in patients with high cardiovascular (CV) risk unable to meet their treatment goals with currently available lipid-lowering therapies.

The target population for this study includes patients with elevated LDL-C who are only able to tolerate low dose or less than low dose of statins (including those not taking a statin due to inability to tolerate a statin) or in combination with other lipid-modifying therapies (in some cases also includes ezetimibe) and who require additional LDL-C lowering.

Elevated LDL-C is a major modifiable risk factor for the development of atherosclerosis and atherosclerotic cardiovascular diseases (ASCVD) [1]. Despite aggressive interventional and pharmacologic therapies, CV disease is the number 1 cause of death globally [2]. An estimated 17.5 million people died from CV diseases in 2012, representing 31% of all deaths worldwide. Of these deaths, an estimated 7.4 million were due to coronary heart disease (CHD) and 6.7 million were due to stroke [2]. Cardiovascular disease remains the leading cause of death among Americans, Europeans, and around the world. The Global Burden of Disease study estimated that 29.6% of all deaths (approximately 15.6 million deaths) were caused by CV disease in 2010, more than all communicable, maternal, neonatal, and nutritional disorders combined, and double the number of deaths caused by cancers [3]. In the United States (US), based on 2011 death rate data, more than 2150 Americans die from CV diseases daily, an average of 1 death every 40 seconds. Approximately 155,000 Americans dying from CV disease are less than 65 years of age. In 2011, 34% of deaths due to CV disease occurred prior to the age of 75 years, less than the current 78.7-year average life expectancy [4].

LDL-C is largely accepted as a valid surrogate endpoint of CV events by clinicians and regulatory authorities [5]. Long-term elevations in LDL-C lead to progressive accumulation of atherosclerotic lesions in the walls of arteries that require long-term management. While lifestyle changes are the primary intervention, these measures rarely decrease plasma LDL-C by >15%. Evidence supporting LDL-C as a therapeutic target and surrogate for CV outcomes comes from interventional studies with LDL-C-lowering therapies, epidemiological studies, genetic variants (both gain of function and loss of function). Large randomized clinical studies aimed at lowering LDL-C show a consistent log-linear relationship between LDL-C reduction and CV risk reduction, independent of the way LDL-C lowering was achieved based on mechanism of action [6,7,8,9]. A published patient-level meta-analysis including 26 trials and more than 160,000 participants, showed a consistent relationship between LDL-C reduction and CV outcomes [7]. This analysis showed that a 1 mmol/L reduction in LDL-C was associated with a 22% reduction in the 5-year incidence of major coronary events, revascularizations, and ischemic strokes. Intensive statin therapy relative to low/moderate intensity statin treatment produces greater benefit in patients at high CV risk [10].

Unfortunately, some patients with elevated LDL-C are unable to take high intensity statins due to dosing limits based on comorbidities, contraindications, and/or tolerance [11]. Nonstatin therapies may provide additional lowering of CV risk as demonstrated in the IMPROVE-IT trial which added ezetimibe to statin therapy [12]. The addition of bempedoic acid to ezetimibe and low intensity statin therapy may offer additional lowering of LDL-C with associated lowering of CV risk. Bempedoic acid has been well tolerated to date and Phase 2 data demonstrate significant LDL-C lowering, prompting further evaluation in Phase 3 clinical studies.

4.2. Background on Bempedoic Acid

4.2.1. Mechanism of Action

Bempedoic acid is a first-in-class small molecule inhibitor of ACL, an enzyme upstream of HMG-CoA in the cholesterol biosynthesis pathway. Bempedoic acid is a prodrug that requires activation in liver to ETC-1002-coenzyme A (ETC-1002-CoA), which mediates competitive inhibition of ACL. Inhibition of ACL by ETC-1002-CoA decreases cholesterol synthesis in the liver leading to increased low-density lipoprotein receptor (LDLR) expression and LDL particle clearance from the blood. Therefore, inhibition of ACL by ETC-1002-CoA decreases LDL-C via the same pathway as HMG-CoA reductase inhibition by statins.

An important differentiating feature of bempedoic acid is that, unlike statins, it does not inhibit cholesterol synthesis in skeletal muscle. The enzyme required to convert bempedoic acid to ETC-1002-CoA is not present in skeletal muscle. Therefore, bempedoic acid is not anticipated to mediate the adverse effects associated with inhibition of biological intermediates within the cholesterol biosynthesis pathway in skeletal muscle; however, the safety of bempedoic acid and its metabolites regarding human skeletal muscle is not yet established.

4.2.2. Nonclinical Experience

[REDACTED]

[REDACTED]

[REDACTED]

[REDACTED]

[REDACTED]

[REDACTED]

4.2.3. Previous Human Experience

The image consists of four identical panels, each featuring a series of horizontal bars. The bars are thick and black, set against a white background. In each panel, there are four distinct horizontal bars. The first bar is positioned at the top, followed by a white space, then a second bar, another white space, and finally a third bar at the bottom. The fourth panel shows a similar pattern but with a slight variation: it has a white bar at the top, followed by a black bar, then a white bar, and finally a black bar at the bottom. This suggests a repeating sequence with a slight variation in the fourth panel.

4.2.4. Dose Selection

the first time in the history of the world, the people of the United States have been called upon to determine whether they will submit to the law of force, or the law of the Constitution. We have said to the world, we will not submit.

4.2.5. Background Therapy

In this study, bempedoic acid is being evaluated as an add-on therapy to ezetimibe for decreasing LDL-C in addition to background low dose or less than low dose statin therapy in patients with elevated LDL-C who require additional LDL-C lowering.

4.2.6. Risk Benefit Summary

To date, the nonclinical and clinical data indicate that bempedoic acid has a favorable risk-benefit profile. The ability of bempedoic acid to achieve clinically meaningful LDL-C-lowering responses while demonstrating a favorable tolerability profile in a variety of patient populations supports continued development of bempedoic acid, an oral ACL inhibitor, in the Phase 3 program.

5. TRIAL OBJECTIVES AND PURPOSE

5.1. Primary Objective

The primary objective of this study is

- To assess the 12-week efficacy of bempedoic acid 180 mg/day versus placebo in decreasing LDL-C when added to ezetimibe therapy in patients with elevated LDL-C

5.2. Secondary Objectives

The secondary objectives of this study are

- To evaluate the effect of 12-week treatment with bempedoic acid 180 mg/day versus placebo when added to ezetimibe therapy on
 - non-high-density lipoprotein cholesterol (non-HDL-C),
 - total cholesterol (TC),
 - apolipoprotein B (apoB), and
 - high-sensitivity C-reactive protein (hs-CRP)
- To evaluate the effect of 12-week treatment with bempedoic acid 180 mg/day versus placebo on TG and HDL-C when added to ezetimibe
- To evaluate 12-week safety and tolerability of bempedoic acid 180 mg/day compared with placebo when added to ezetimibe

5.3. Tertiary Objectives

The tertiary objectives of this study are

- To evaluate the effects of treatment with bempedoic acid 180 mg/day versus placebo when added to ezetimibe therapy at Weeks 4 and 8 on:
 - LDL-C
 - Non-HDL-C
 - TC
 - TG
 - HDL-C

5.4. Study Endpoints

5.4.1. Primary Efficacy Endpoint

The primary efficacy endpoint is the percent change from baseline to Week 12 in LDL-C.

5.4.2. Secondary Efficacy Endpoints

Secondary efficacy endpoints (specific to stepdown approach [[Section 12.6](#)]) are

1. Percent change from baseline to Week 12 in
 - a. non-HDL-C
 - b. TC
 - c. apoB
 - d. hs-CRP

Other secondary efficacy endpoints are

2. Percent change from baseline to Week 12 in
 - a. TG
 - b. HDL-C

5.4.3. Tertiary Efficacy Endpoints

Tertiary endpoints include assessments of percent change and absolute change from baseline in lipid levels at the additional time points of Week 4 (T2) and Week 8 (T3).

1. Percent change from baseline to Weeks 4 and 8 in
 - a. LDL-C
 - b. Non-HDL-C
 - c. TC
 - d. TG
 - e. HDL-C
2. Absolute change from baseline to Weeks 4, 8, and 12 in LDL-C.

5.4.4. Safety Endpoints

- a. Subject incidence to TEAE
- b. Safety laboratory values and vital signs
- c. ECG findings
- d. Cardiovascular event rates

6. INVESTIGATIONAL PLAN

6.1. Overall Study Design

This is a Phase 3, randomized, double-blind, placebo-controlled, parallel group study evaluating the efficacy and safety of bempedoic acid as an add-on therapy to ezetimibe in patients with elevated LDL-C.

Screening Week -5 (Visit S1) will begin approximately 5 weeks prior to randomization, but can be extended for an additional 4 weeks, if needed, to adjust background medical therapy or for other reasons as specified in the protocol. Eligible patients will return to the clinical site at Week -4 (Visit S2) to begin treatment with study supplied ezetimibe 10 mg and single-blind placebo. Patients having their own supply of ezetimibe will switch to study-supplied ezetimibe at this visit.

6.2. Study Hypothesis

The study will assess the 12-week efficacy of bempedoic acid as an add-on therapy to ezetimibe in decreasing LDL-C versus placebo. The treatment duration of 12 weeks and study population of 225 patients will provide data on the lipid profile, safety, and tolerability of bempedoic acid in patients with elevated LDL-C who have a need for additional lipid-lowering therapy.

6.3. Study Duration and Period

The expected total duration of study participation for each randomized patient is approximately 17 weeks. The study will consist of an approximately 1-week screening period, a 4-week placebo run-in period, and a 12-week of treatment period.

6.4. End of Study

The study will end when the last randomized patient completes the Week 12 visit. The estimated overall duration of the study (first patient first visit [FPFV] to last patient last visit [LPLV]) is approximately 11 months.

6.5. Number of Patients

Approximately 225 eligible patients will be randomized 2:1 on Day 1 (Visit T1) to receive either bempedoic acid 180 mg (N = 150) or placebo (N = 75) for 12 weeks.

6.6. Patient Identification Numbers

A unique patient identification number will be assigned to identify each patient throughout the study and will be entered on all documentation. If a patient is not eligible to receive treatment, or if a patient discontinues from the study, their patient identification number cannot be assigned to another patient.

Patient identification numbers will be assigned sequentially by interactive web response system (IWRS) at the time of informed consent during the screening module transaction.

6.6.1. Screening and Placebo Run-in Period

Screening will occur approximately 5 weeks prior to Day 1 (Visit T1) when the patient's eligibility will be evaluated. Eligible patients who are taking concomitant medications must be on stable regimens as defined in [Section 7.1](#). At the investigator's discretion, screening may be extended for an additional 4 weeks, if needed, to adjust background medical therapy or for other reasons as specified in the protocol. Eligible patients will return to the clinical site at Week -4 (Visit S2) to initiate administration of open label ezetimibe and single-blind placebo. Eligible patients will return at Week -1 (Visit S3) for basic fasting lipids assessments and an assessment of tolerability and study drug adherence (see [Section 7](#) for eligibility criteria). Patients who are deemed not eligible for randomization at any point during screening will be notified by clinical site personnel regarding their eligibility status and considered screen failures. As necessary, for reasons of safety if a patient begins the run-in period but fails screening prior to randomization, the patient may be asked to return to the clinical site for further evaluation and follow-up of AEs.

6.6.2. Randomization and Treatment Periods

For patients who satisfy all entry criteria and complete the 1-week screening period and 4-week run-in period, randomization to a treatment group will occur via IWRS at Week 0 (Visit T1). Approximately 225 patients will be randomized in a ratio of 2:1 to receive 1 of the 2 following treatments in a double-blind fashion:

- Bempedoic acid 180-mg tablet
- Matching placebo tablet

7. SELECTION AND WITHDRAWAL OF PATIENTS

7.1. Subject Inclusion Criteria

Each potential patient must satisfy all of the following criteria to be enrolled in the study.

1. Provision of written informed consent prior to any study-specific procedure
2. Age ≥ 18 years or legal age of majority based on regional law, whichever is greater, at Week -5 (Visit S1)
3. Fasting (minimum of 10 hours) calculated LDL-C at Week -5 (Visit S1) as defined by ezetimibe use at screening:
 - For patients who have been taking ezetimibe 10 mg daily prior to Week -5 (Visit S1): Fasting LDL-C ≥ 100 mg/dL (2.6 mmol/L) on stable background lipid-modifying therapy (LMT; greater than or equal to 4 weeks prior to screening)
 - For patients who have not been taking ezetimibe Week -5 (Visit S1): Fasting LDL-C ≥ 120 mg/dL (3.1 mmol/L) on stable background LMT (greater than or equal to 4 weeks prior to screening).
 - All patients must have fasting LDL-C ≥ 70 mg/dL (1.8 mmol/L) at Week -1 (Visit S3)
4. Currently receiving stable (greater than or equal to 4 weeks prior to screening) background statin dose that does not exceed low dose statin therapy. Patients must report attempting statin therapy and being unable to tolerate it due to an adverse safety effect that started or increased during statin therapy and resolved or improved when statin therapy was discontinued or the dose lowered.

Low dose statin therapy is defined as an average daily dose of rosuvastatin 5 mg, atorvastatin 10 mg, simvastatin 10 mg, lovastatin 20 mg, pravastatin 40 mg, fluvastatin 40 mg, or pitavastatin 2 mg.

Very low dose statin therapy is defined as an average daily dose of rosuvastatin <5 mg, atorvastatin <10 mg, simvastatin <10 mg, lovastatin <20 mg, pravastatin <40 mg, fluvastatin <40 mg, or pitavastatin <2 mg.

Patients on low or very low dose statin or unable to tolerate any statin at any dose are eligible. Patients may continue taking low or very low dose statin therapy throughout the study provided that it is stable (greater than or equal to 4 weeks) and well tolerated.

Patients unable to take any dose of statins are also eligible provided that statin therapy has been attempted as described above.

5. Men and nonpregnant, nonlactating women. Women must be either
 - Naturally postmenopausal defined as ≥ 1 year without menses and
 - ≥ 55 years, or
 - <55 years with follicle-stimulating hormone (FSH) ≥ 40.0 IU/L, or
 - Surgically sterile including hysterectomy, bilateral oophorectomy, and/or tubal ligation, or

- Women of childbearing potential willing to use 2 acceptable methods of birth control (unless they have agreed to follow the definition of true abstinence). The minimal requirement for adequate contraception should be started on Day 1, continuing during the study period and for at least 30 days after the last dose of study drug. Acceptable methods of birth control include:
 - oral, implantable, injectable, or topical birth control medications
 - placement of an intrauterine device with or without hormones
 - barrier methods including condom or occlusive cap with spermicidal foam or spermicidal jelly
 - vasectomized male partner who is the sole partner for this patient
 - True abstinence: When this is in line with the preferred and usual lifestyle of the subject. (Periodic abstinence [eg, calendar, ovulation, symptothermal, postovulation methods], declaration of abstinence for the duration of a trial, and withdrawal are not acceptable methods of contraception).

Note: There are no protocol-specific birth control requirements for men with partners who are able to become pregnant.

7.2. Subject Exclusion Criteria

Patients who meet any of the following criteria are not eligible:

1. Body mass index (BMI) $>50 \text{ kg/m}^2$
2. Recent history of documented clinically significant cardiovascular disease including, but not limited to
 - Within 3 months of screening (Week -5 [Visit S1]) or between screening and randomization, myocardial infarction, severe or unstable angina pectoris, coronary angioplasty, coronary artery bypass graft, stroke, transient ischemic attack, cerebrovascular event, symptomatic carotid artery disease, or symptomatic peripheral arterial disease
 - Uncontrolled hypertension, defined as sitting systolic blood pressure (SBP) $\geq 160 \text{ mm Hg}$ and diastolic blood pressure (DBP) $\geq 100 \text{ mm Hg}$ after sitting quietly for 5 minutes. Note: If the initial blood pressure (BP) values meet or exceed the specified level, an additional BP assessment may be completed. If the systolic or the diastolic values continue to meet or exceed the threshold, the patient may not continue screening. However, at the discretion of the investigator, the screening period may be extended up to 4 weeks to allow for a repeat qualifying BP assessment following adjustment of BP medication(s), provided that the patient has been on a stable dose of the BP medication for a minimum of 2 weeks prior to randomization and the repeat BP measurements do not meet the exclusion criteria
 - Within 3 months of screening (Week -5 [Visit S1]) or between screening and randomization visits, arrhythmia requiring medical intervention.

- Planned revascularization procedures
- New York Heart Association (NYHA) Class IV heart failure

3. Total fasting (minimum of 10 hours) TG ≥ 500 mg/dL (5.6 mmol/L) at Week -5 (Visit S1)
Note: TG may be repeated 1 time with the screening period extended up to 4 weeks. For those patients who have a repeat TG, the repeat value will be used to determine eligibility.

4. Glycosylated hemoglobin, Type A_{1C} (HbA_{1C}) $\geq 10\%$ at Week -5 (Visit S1)

5. Persistent poor adherence with study-supplied ezetimibe and/or single-blind placebo study drug (ie, ingesting <80% of planned doses) or lack of tolerance to run-in medications assessed prior to randomization.

6. Uncontrolled hypothyroidism, including thyroid-stimulating hormone (TSH) $> 1.5 \times$ the upper limit of normal (ULN) at Week -5 (Visit S1);

7. Liver disease or dysfunction, including:

- Positive serology for hepatitis B surface antigen (HBsAg) and/or hepatitis C antibodies (HCV-ABVivi) at Week -4 (Visit S2), or
- Alanine aminotransferase (ALT) and/or aspartate aminotransferase (AST) $\geq 2.0 \times$ ULN at Week -5 (Visit S1). If total bilirubin (TB) $\geq 1.2 \times$ ULN, a reflex indirect (unconjugated) bilirubin will be obtained, and if consistent with Gilbert's disease or if the patient has a history of Gilbert's Disease, the patient may be enrolled in the study.

Note: At the discretion of the investigator, a single repeat of ALT and/or AST may be completed prior to randomization. For those patients who have a repeat ALT and/or AST, the repeat value will be used to determine eligibility. Also, if test for hepatitis C antibody is positive, but optional reflexive test for hepatitis C ribonucleic acid (RNA) is negative, the patient can be enrolled.

8. Renal dysfunction or glomerulonephritis, including estimated glomerular filtration rate (eGFR; using central laboratory determined Modification of Diet in Renal Disease [MDRD] formula) < 30 mL/min at Week -5 (Visit S1). Note, a single repeat qualifying eGFR, performed at the discretion of the investigator, is acceptable;

9. Gastrointestinal conditions or procedures (including weight loss surgery; eg, Lap-Band[®] or gastric bypass) that may affect drug absorption;

10. Hematologic or coagulation disorders or a hemoglobin (Hgb) level < 10.0 g/dL at Week -5 (Visit S1);

11. Active malignancy, including those requiring surgery, chemotherapy, and/or radiation in the past 5 years. Nonmetastatic basal or squamous cell carcinoma of the skin and cervical carcinoma in situ are allowed

12. Unexplained creatine kinase (CK) $> 3 \times$ ULN at any time prior to randomization (ie, not associated with recent trauma or physically strenuous activity). Patients with an explained CK elevation must have single repeat CK $\leq 3 \times$ ULN prior to randomization;

13. History of drug or alcohol abuse within the last 2 years or reported current consumption of >14 alcoholic drinks/week, or any illicit drug use, history of amphetamine and derivatives abuse or cocaine abuse. Subjects with amphetamine derivatives prescribed by and under the care of a health care practitioner can be enrolled after evaluation by the investigator;
14. Blood donation, participation in a multiple blood draws, clinical study, major trauma, blood transfusion or surgery with or without blood loss within 30 days prior to randomization;
15. Use of any experimental or investigational drugs within 30 days prior to screening. Patients who have enrolled in a study of an experimental small interfering RNA (siRNA) inhibitor of PCSK9 are excluded;
16. Previous enrollment in a bempedoic acid clinical study.
17. Use of any of the following drugs prior to screening (Week -5, Visit S1) or a plan to use these drugs during the study as follows:
 - Within 2 weeks prior to screening
 - Cholestin or red yeast rice-containing products (also known as monascus purpureus extract)
 - Within 4 weeks prior to screening
 - Statin doses exceeding those defined as low dose. Doses exceeding low dose statin therapy are defined as an average daily dose of rosuvastatin greater than 5 mg, atorvastatin greater than 10 mg, simvastatin greater than 10 mg, lovastatin greater than 20 mg, pravastatin greater than 40 mg, fluvastatin greater than 40 mg, or pitavastatin greater than 2 mg.
 - Within 6 weeks prior to screening for patients taking a statin
 - Gemfibrozil is not allowed in patients taking a statin as per co-administration instructions defined in the statin label
 - Within 3 months prior to screening:
 - Lomitapide or apheresis therapy
 - Probenecid or cyclosporine
 - Within 4 months prior to screening
 - Proprotein convertase subtilisin/kexin type 9 (PCSK9) inhibitors
 - Within 6 months prior to screening
 - Mipomersen
 - Cholesteryl ester transfer protein inhibitor (CETP-I) within the last 2 years prior to screening (Week -5, Visit S1) except for evaceptrapib within the last 3 months to screening (Week -5, Visit S1)

18. Planned initiation of the following drugs during the clinical trial or changes to the following drugs prior to randomization:

- Hormone replacement (within 6 weeks prior to randomization)
- Thyroid replacement (within 6 weeks prior to randomization)
- Diabetes medications (within 4 weeks prior to randomization)
- Obesity medication (4 weeks prior to randomization)

19. New or planned dose changes of systemic corticosteroids.

Note: Stable doses of systemic corticosteroids at screening are allowed (≥ 4 weeks from Visit S1). Topical steroids are allowed.

20. An employee or contractor of the facility conducting the study, or a family member of the principal investigator, co-investigator, or Sponsor.

21. Pregnant, breastfeeding, or intending to become pregnant within 30 days after study completion or last dose of study drug.

22. Previous intolerance to ezetimibe.

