--	--

Exclusion Criteria:

Patients who meet any of the exclusion criteria are not eligible. Selected exclusion criteria are listed below; all exclusion criteria are listed in the protocol body.

1. Body mass index (BMI) >50 kg/m²
2. Recent history of documented clinically significant cardiovascular disease including, but not limited to
 - Within 3 months of screening (Week -5 [Visit S1]) or between screening and randomization

visits: MI, severe or unstable angina pectoris, coronary angioplasty, coronary artery bypass graft, stroke, transient ischemic attack, cerebrovascular event, symptomatic carotid artery disease, or symptomatic peripheral arterial disease.

- Uncontrolled hypertension, defined as sitting systolic blood pressure (SBP) ≥ 160 mm Hg and diastolic blood pressure (DBP) ≥ 100 mm Hg after sitting quietly for 5 minutes. Note: If the initial blood pressure (BP) values meet or exceed the specified level, an additional BP assessment may be completed. If the systolic or the diastolic values continue to meet or exceed the threshold, the patient may not continue screening. However, at the discretion of the investigator, the screening period may be extended up to 4 weeks to allow for a repeat qualifying BP assessment following adjustment of BP medication(s), provided that the patient has been on a stable dose of the BP medication for a minimum of 2 weeks prior to randomization and the repeat BP measurements do not meet the exclusion criteria
- Within 3 months of screening [Week -5 (Visit S1)] or between screening and randomization visits, an arrhythmia requiring medical intervention.
- Planned revascularization procedures
- New York Heart Association (NYHA) Class IV heart failure

3. Total fasting (minimum of 10 hours) TG ≥ 500 mg/dL (5.6 mmol/L) at Week -5 (S1)
Note: TG may be repeated 1 time with the screening period extended up to 4 weeks. For those patients who have a repeat TG, the repeat value will be used to determine eligibility.

4. Hemoglobin A_{1C} (HbA_{1C}) $\geq 10\%$ at Week -5 (Visit S1)

5. Persistent poor adherence with study-supplied ezetimibe and/or single-blind, placebo study drug (ie, ingesting $<80\%$ of planned doses) or lack of tolerance to run-in medications assessed prior to randomization.

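### Exclusion criterion 2 requires both blood pressures to be raised, but its own retest note stops the patient if either one is; the definition should read 'or'

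*Protocol*

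**What the plan says.** The blood pressure bullet of exclusion criterion 2 (Protocol Section 7.2) has four parts.

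- **Definition.** The systolic threshold (160 mm Hg) is joined to the diastolic threshold (100 mm Hg) by the words "and diastolic blood pressure (DBP", so both are required.
- **Retest trigger.** If the initial "values meet or exceed the specified level, an additional BP assessment may be completed". The level referred to is the one just defined.
- **Stop rule.** "If the systolic or the diastolic values continue to meet or exceed the threshold, the patient may not continue screening". Either component is enough.
- **Route back.** However, "at the discretion of the investigator, the screening period may be extended up to 4 weeks" so that medication can be adjusted, on condition that the dose has been stable for at least 2 weeks before randomization and "the repeat BP measurements do not meet the exclusion criteria".

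The synopsis has the same definition ("mm Hg and diastolic blood pressure (DBP") and the same stop rule, so it does not settle which governs. The bullet sits under a parent criterion worded "Recent history of documented clinically significant cardiovascular disease including, but not limited to". Blood pressure is recorded at every visit before randomization (S1, S2, S3 and T1; Appendix 1), and the safety endpoints in Section 5.4.4 include vital signs and "Cardiovascular event rates".

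**The concern.** One bullet holds two rules for the same measurement. The definition and the trigger need both pressures to be raised; the stop rule needs only one. The re-entry condition points back to the exclusion criteria, which most naturally means the two-component definition again.

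Two things are at stake. First, the written rule does not catch severe elevation of a single component, so excluding such a patient depends on investigator judgment. Second, the same reading can bar one patient and not another, depending on whether it was the first or the repeat measurement. In a multicenter trial a numeric threshold is there to give every site one rule, and this one can be applied in two ways.

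**Working it through.** No figure in the protocol has to be reproduced here. The check is one of logic, using only the thresholds in Section 7.2.

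**Step 1. Classify a single reading.** Let S = 1 if systolic ≥ 160 and D = 1 if diastolic ≥ 100. The definition is met when S and D are both 1. The stop rule is met when at least one of them is 1.

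| S | D | Definition (*and*) | Stop rule (*or*) | Agree? |
|---|---|---|---|---|
| 1 | 1 | met | met | yes |
| 1 | 0 | not met | met | no |
| 0 | 1 | not met | met | no |
| 0 | 0 | not met | not met | yes |

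The definition covers 1 of 4 patterns and the stop rule 3 of 4, so they differ on 3 − 1 = 2 of 4. This counts patterns, which are not equally likely. It is not a share of patients.

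**Step 2. Follow patients through the text as written.**

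- First reading 190/95: S = 1, D = 0. The definition is not met, so there is no retest and the blood pressure rule does not exclude the patient.
- First reading 165/102: S = 1, D = 1. The definition is met and a retest is offered. Retest 150/101: S = 0, D = 1. The stop rule is met and the patient may not continue, unless the extension of up to 4 weeks is used. Had 150/101 been the first reading, the definition would not have been met.
- First reading 165/105, retest 165/90: stopped by the note. Suppose the patient then takes the extension and again measures 165/90. Judged against the two-component definition, this reading does not meet the exclusion, so the value that barred the patient would readmit the patient.

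**Step 3. Pair each first-reading pattern with each repeat pattern.** After a first reading with both components raised, the definition and the note give different answers for 2 of the 4 possible repeats (systolic only, diastolic only). After a first reading with only one component raised, the literal text excludes nobody, whatever a repeat might show, because no retest is triggered.

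**Step 4. Repeat with *or* in the definition.** Definition and stop rule agree on 4 of 4 patterns. A patient with at least one component at threshold on both the first and the repeat reading is stopped; a patient with both below threshold at the repeat is not. The 190/95 patient is retested, and 165/90 after the extension no longer qualifies for re-entry.

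**The case against.** The strongest reply is that the bullet can be read as a two-stage rule: both components must be raised to trigger action, and both must come down to clear it. A stricter standard for clearing than for triggering is workable, and treating 150/101 differently at first reading and at retest is what such a rule would do. But the protocol nowhere states this intent, and the reading fails at the re-entry condition, where the test reverts to the two-component definition.

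Other points carry weight:

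- *Intent.* The protocol does not say that *or* was meant. Changing the note to *and* would also make the bullet consistent. Preferring *or* rests on the stop rule and on the clinical view that a reading such as 190/95 should not pass. The liver criterion in the same section uses and/or where either enzyme suffices, so sites have reason to take a bare *and* literally.
- *Discretion.* The parent criterion is open-ended, blood pressure is checked at every visit, and under Section 10.3.1 the investigator can interrupt treatment of a patient at risk. This softens the safety consequence but leaves the written rule uncorrected.
- *Over-exclusion.* The 150/101 retest case is largely handled by the medication-adjustment extension.
- *Size.* The visible text names no blood pressure effect of bempedoic acid, and the number of patients involved is unknown.

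**Conclusion.** The concern holds. The definition and the stop rule in exclusion criterion 2 conflict on isolated systolic and isolated diastolic elevation, and no other current text in the protocol resolves it. The conclusion rests on reading *and* and *or* literally, on taking the retest trigger and the re-entry condition as references to the definition, and on the inference that the stop rule shows the intended rule. The effect is confined to consistent eligibility and patient safety; it has no bearing on the primary analysis, power or type I error. The correction should be made, but the trial's main inference does not depend on it.

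**What to change.** In Section 7.2 and in the synopsis, define uncontrolled hypertension as sitting systolic pressure ≥ 160 mm Hg **or** diastolic pressure ≥ 100 mm Hg. The stop rule already uses *or*, and the trigger and the re-entry condition then refer to the same rule without further editing. Using *and* throughout would also be consistent but would still let 190/95 through, so it is not recommended.

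The cost is one word in two places and a clarification to sites. Somewhat more patients will need a retest or fail screening, and some of those will be recovered through the existing extension of up to 4 weeks. Visits, laboratory tests, sample size and analysis do not change.
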